## 4 OVERALL STUDY DESIGN

## 4.1 Overview of Study Design

This is a Phase 3, randomised, parallel-group, placebo-controlled, double-masked, multicentre study to assess the efficacy and safety of clobetasol propionate ophthalmic nanoemulsion 0.05% in the treatment of inflammation and pain associated with cataract surgery.

All randomized patients will undergo routine cataract surgery according to the investigator's normal procedures being surgery day considered Day -1 of the study, whereas the day of the randomization/first administration will be considered study Day 1. First administration of the Investigational Medicinal Product (IMP) will take place at the study center, whereas the rest of study medication will be dispensed to patients for self-administration at a dosage of one drop every six hours, four times a day (QID) during 14 days as well as a diary to record the drug instillations.

Figure 1. Diagram of Study Design

\* Patients who, for any reason, withdraw from the study treatment will be highly encouraged to continue attending all their remaining study visits to collect the most complete efficacy and safety data.

#### 4.2 Determination of Sample Size

At least 210 patients from approximately 20 sites in the U.S. will participate in this study. Patients will be randomized in a 2:1 ratio to receive either clobetasol propionate ophthalmic nanoemulsion 0.05 % (N=140) or placebo (N=70) for the treatment of inflammation and pain associated with cataract surgery. Dropouts will not be replaced since the expected dropout rate is low (4%).

The sample size calculation is based on a two group  $\chi^2$  test with a 0.05 two-sided significance level will have 80% power to detect the difference between a proportion with complete resolution of anterior chamber cells in the active group of 0.22 and the placebo group proportion of 0.07 (odds ratio of 3.747) when the sample size is 202.

#### 5 DATA SETS TO BE ANALYSED

The following analysis sets will be used for the statistical analysis and presentation of data:

- **Full Analysis Set (FAS):** The FAS will be the primary analysis set for the efficacy endpoints and will include all randomized patients. The FAS population will be analyzed according to the planned treatment (rather than treatment actually received).

- **Safety Analysis (SAF) set** The safety set will be the primary analysis set for the safety endpoints and will include all randomized patients who instilled at least one dose of IMP or placebo. The SAF will be analyzed according to the treatment actually received.
- **Per Protocol (PP) Population:** The PP population set will be tested to confirm the robustness of the efficacy analyses and will include all patients in the FAS who have no major protocol deviations (i.e. patients who comply the protocol sufficiently to ensure that the data exhibits the effects of the IMP or placebo when administered as intended). Protocol violations include: violations of entry criteria, lack of compliance and the use of prohibited medication. The PP population will be analyzed according to the treatment actually received.

Lack of compliance is defined as less than 80% compliance (section 6.3.8).

Efficacy analyses will be based on both the FAS and the PP, but the FAS will be considered the primary analysis population.

Safety analyses will be based on the SAF.

For the efficacy endpoints only visits with IMP and without prohibited/rescue medication will be analyzed for FAS population.

For the efficacy endpoints based in PP population (primary efficacy analysis and key secondary at visit 3) will include all patients in the FAS population who have no major protocol deviations. Without violations of eligibility criteria, lack of compliance at visit 3 (see section 6.3.8 for details) and without the use of rescue/prohibited medication until visit 3.

Only study eye will be analyzed and presented in tables and the non-study eye will only be included in listings.

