	
IMP when administered as intended). Protocol violations include: violations of entry criteria, lack of compliance and the use of prohibited medication. The PP population will be analyzed according to the treatment actually received.
 
Efficacy analyses will be based on both the FAS and the PP, but the FAS will be considered the primary analysis population.
 
Safety analyses will be based on the safety set.
 
Summary statistics
 
In general, data will be summarized by means of summary statistics. Continuous data will be presented with the number of observations, mean value, confidence intervals, standard deviation, minimum, Q1, median, Q3 and maximum value. Change from baseline to each post-baseline visit will be also described using descriptive statistics. Categorical data will be presented as counts and percentages.
 
The data will be presented for each treatment group by visit.
 
Individual patient data will be listed for all enrolled patients. Listings will be sorted by center and patient number and labelled by randomized treatment group.
 
Missing data
 
Data not collected after rescue therapy has been initiated will not be considered missing since the primary measure is a responder measure where rescue is considered treatment failure. Patients with missing data for the analysis of the primary endpoint will be assigned the status of treatment failure.
 
Primary analysis
 
The aim of the primary analysis of this study is to assess the superiority of clobetasol propionate ophthalmic nanoemulsion 0.05% compared to placebo with respect to the primary endpoint in the FAS.
 
The primary analysis will be based on a single study eye for each patient. Each patient's study eye will be defined as the surgery eye.
 
The test will be the proportion of study eyes with complete clearing of anterior chamber cells (count cell = 0) at Visit 3 (Day 8 ± 1 day) without receiving rescue medication as compared between clobetasol propionate ophthalmic nanoemulsion 0.05% dosed QID and placebo dosed QID using the chi square statistic.
 
The PP population set will be also tested to confirm the robustness of the primary analysis.
 
Key Secondary Analysis
 
The aim of the key secondary analysis of this study is to assess the superiority of clobetasol propionate ophthalmic nanoemulsion 0.05% compared to placebo with respect to the key secondary endpoint in the FAS.
 
The key secondary analysis will be based on a single study eye for each patient. Each patient's study eye will be defined as the surgery eye.

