### 5.3 **Withdrawal, Premature Discontinuation of Study Medication, and Replacement of Patients**

Patients are free to discontinue their participation in the study at any time. Additionally, patients may be withdrawn from study at any time, if deemed necessary by the investigator

(after discussion with the Medical Monitor). Withdrawal from the study will not affect or prejudice the patients' further care or treatment.

Potential reasons for withdrawal of patients from this study are:

- The decision of a patient to withdraw informed consent
- Patient is lost to follow-up (Section [5.3.1](#))
- Potential reasons for premature discontinuation of study medication include, but are not limited to: Occurrence of a treatment-emergent AE (TEAE) or considerable worsening of an AE that, in the opinion of the investigator in consultation with the Medical Monitor and Sponsor, represents an unacceptable risk to the patient if he/she continues to receive study medication. The investigator must follow the patient until the AE resolves or satisfactorily stabilizes
- Administration of a rescue medication. Any patient placed on rescue therapy will discontinue the use of the IMP (see Sections [6.7.1](#) and [6.7.2](#))
- Patient's failure to comply with protocol requirements or study related procedures
- In case of pregnancy. The investigator will continue the follow-up of the patient until the end of the pregnancy
- Any surgery (different from the actual routine cataract surgery on the study eye) in the study or contralateral eye

In any case of premature discontinuation of study medication, the investigator must make extensive efforts to ensure that the patient will attend all his/her remaining study visits until study completion (at Visit 5), aiming to collect the most complete efficacy and safety data.

The reason and date the patient is withdrawn from the study will be documented in the eCRF (e.g. lost to follow-up, consent withdrawn, AEs, etc.).

If a patient is withdrawn from the study, the investigator should attempt to complete all discharge procedures (including the Early Termination Visit; Section [4.3.2.8](#)). All AEs should be followed up according to Section [8.3.6](#).

If a patient is withdrawn from the study, or withdraw his/her consent, all data collected until the time of withdrawal will be used in the analyses, unless this is prohibited by local regulations.

Patients who drop out from the study will not be replaced.

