### 6.7.2 Rescue Medication

Any patients not responding adequately to the IMP may be rescued and placed on alternate therapy (Section [6.7](#)) at the investigator's discretion at any time.

The choice of rescue medication is at the investigator's discretion. Any patient placed on rescue therapy will discontinue the use of the IMP and the investigator must make extensive efforts to ensure that the patient will attend all his/her remaining study visits until study completion, aiming to collect the most complete efficacy and safety data.

Additionally, patients will be asked to phone the study center at any time to speak to a member of the medical personnel should they experience any worsening of ocular conditions or other AEs.

Rescued patients will be considered treatment failures, but the need for rescue therapy will not be considered an AE.

---

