#### 9.1.3 *Missing, Unused, and Spurious Data*

Any missing, unused, or spurious data will be noted in the final clinical study report (CSR) and presented in the data listings.

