### **6.3.5 Primary Efficacy analysis**

The primary efficacy endpoint in this clinical trial is the proportion of patients with anterior chamber cell grade of "0" (absence of cells) compared to placebo at Day 8.

The statistical hypothesis that will be tested for primary efficacy is described as:

- Null Hypothesis ( $H_0$ ): The difference in proportion of patients with anterior chamber cell grade of "0" at Day 8 between treatment regimes = 0.
- Alternative Hypothesis ( $H_1$ ): The difference in proportion of patients with anterior chamber cell grade of "0" at Day 8 between treatment regimes  $\neq 0$ .

The aim of the primary analysis of this study is to assess the superiority of clobetasol propionate ophthalmic nanoemulsion 0.05% compared to placebo with respect to the primary efficacy endpoint. The primary analysis will be based on a single study eye for each patient. Each patient's study eye will be defined as the surgery eye.

A Chi-Square test will be employed to test the proportion of study eyes with complete clearing of anterior chamber cells (count cell = 0) at Visit 3 (Day 8  $\pm$  1 day) without receiving rescue medication as compared between clobetasol propionate ophthalmic nanoemulsion 0.05% dosed QID and placebo dosed QID. The proportion of eyes with absence of cells (anterior chamber cell grade=0) together with its 95% confidence interval (CI) will be presented. Analysis will be conducted both in FAS and PP to test the robustness of the results.

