### 6.6 Handling of Dropouts and Missing Data

No missing imputation methods are foreseen. As described in the CSP, any missing, unused, or spurious data will be noted in the final Clinical Study Report (CSR) and presented in the data listings.

In all listings, missing or incomplete dates should be left as they have been recorded. However, for calculation / sorting / assignation based on dates, the following method will be

used, in the event that any date is incomplete after Data Management processing and this date needs to be used for calculation:

- if no field is available: no imputation will be performed,
- if only the year is available: Day “01” and month of “July” will be imputed,
- if the month and year are available: Day “15” will be imputed.

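### The SAP's on-treatment, no-rescue visit filter with no imputation contradicts the protocol's failure rules, leaving the Day 8 denominator unsettled for the primary and key secondary tests

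*SAP*

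**What the plan says.** **Protocol.** Section 9.1.4 puts every randomized patient in the FAS, analysed by planned treatment. Section 6.7.2 says "Rescued patients will be considered treatment failures", and the synopsis agrees: data absent after rescue are not regarded as missing, "since the primary measure is a responder measure where rescue is considered treatment failure". The synopsis also states: "Patients with missing data for the analysis of the primary endpoint will be assigned the status of treatment failure". Together these fix the Day 8 denominators at 140 and 70. The body of the protocol does not repeat the missing-data rule. Section 9.1.3 says only "Any missing, unused, or spurious data will be noted in the final clinical study report (CSR) and presented in the data listings".

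**SAP.** Section 5 repeats the all-randomized FAS definition, then adds "For the efficacy endpoints only visits with IMP and without prohibited/rescue medication will be analyzed for FAS population". Section 6.6 says "No missing imputation methods are foreseen" and cites the protocol, but takes over only the content of 9.1.3. Section 6.3.5 tests clearing of cells at Visit 3 "without receiving rescue medication as compared between clobetasol propionate ophthalmic nanoemulsion 0.05% dosed QID and placebo dosed QID"; section 6.3.6.1 uses the same wording for pain. Neither says what becomes of a rescued, off-drug or missing patient in the denominator.

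**Follow-up.** After early stopping of study drug, protocol 5.3 says "the investigator must make extensive efforts to ensure that the patient will attend all his/her remaining study visits until study completion", so that efficacy data are as complete as possible.

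**The concern.** The FAS is all randomized patients by definition, but the SAP filter selects on events after randomization. Four kinds of patient are affected at Day 8:

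- **Rescued.** Failures under the protocol. Under SAP section 5 their visits are not analysed, while SAP 6.3.5 and 6.3.6.1 can be read as making rescue a non-response. The SAP therefore conflicts with itself as well as with the protocol.
- **Missing Visit 3.** Failures under the synopsis. No SAP text restores that rule.
- **Off study drug, not rescued.** The protocol does not call them failures and asks for their visits. The SAP discards those observations.
- **Prohibited medication not classed as rescue.** SAP 6.3.9 separates this category and section 5 filters it out. The protocol gives it no responder status in the FAS.

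If these events depend on treatment, the patients left no longer form the randomized groups. The same ambiguity reaches the key secondary endpoint. Taken literally, the filter also removes every Day 29 visit, because dosing lasts 14 days. SAP section 8.1 plans Day 29 tables in the FAS, so that was probably not intended, but it shows the sentence cannot be applied as written.

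**Working it through.** **Inputs.** Protocol 9.1.1 and SAP 4.2: response 0.22 against 0.07, two-sided 0.05, 80% power, 202 evaluable, 4% loss, 140/70 randomized. The share of patients removed at Day 8 is given nowhere beyond the 4% loss, so all other removal rates below are assumptions.

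**Step 1: reproduce the plan.** With k = 2 and mean rate (0.07 + 2 × 0.22)/3 = 0.17:

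n(placebo) = [1.96·√(1.5 × 0.17 × 0.83) + 0.842·√(0.07 × 0.93 + 0.22 × 0.78/2)]² / 0.15² = (0.902 + 0.327)² / 0.0225 ≈ 67.1, rounded up to 68, so 204 in total against the stated 202.

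Approximate power at 202 is 80.2%. The odds ratio (0.22/0.78)/(0.07/0.93) = 3.747 is exact, and 202/0.96 = 210.4. The sample size is sound; the issue is the denominator.

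**Step 2: compare the rules when everyone removed is a failure (rescued or missing).** If a fraction r of an arm is removed and none of them responded, the rate becomes p/(1 − r) and the arm size n(1 − r), rounded. At 5%/20%, for example, 0.22/0.95 = 23.2% of 133 is compared with 0.07/0.80 = 8.75% of 56. Power is by exact binomial enumeration of the uncorrected chi-square test.

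| Removed, clobetasol / placebo | Sizes | Difference (points) | Power |
|---|---|---|---|
| none (failures counted) | 140/70 | 15.0 | 83.4% |
| 4% / 4% | 134/67 | 15.6 | 83.5% |
| 10% / 10% | 126/63 | 16.7 | 84.8% |
| 4% / 8% | 134/64 | 15.3 | 80.4% |
| 3% / 10% | 136/63 | 14.9 | 76.9% |
| 5% / 20% | 133/56 | 14.4 | 68.4% |
| 10% / 4% | 126/67 | 17.2 | 88.9% |
| 20% / 5% | 112/66 | 20.1 | 94.2% |

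On one planned data set, with 31 responders on clobetasol and 5 on placebo, 31/140 against 5/70 gives p = 0.0066. At 4%/4%, 31/134 against 5/67 gives p = 0.0063. At 5%/20%, 31/133 against 5/56 gives p = 0.022.

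**Step 3: removed patients are off drug, not rescued, and respond at their arm's rate.** The difference stays at 15.0 points but patients are lost: 5%/5% (133/66) gives 81.3% power and 10%/10% (126/63) gives 79.7%.

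**Step 4: error rate when both arms truly respond at 7%.**

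| Removed, clobetasol / placebo | Total | Favouring clobetasol | Favouring placebo |
|---|---|---|---|
| none (failures counted) | 4.7% | 2.0% | 2.7% |
| 5% / 20% | 7.3% | 0.8% | 6.5% |
| 20% / 5% | 5.6% | 4.6% | 1.0% |

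Equal removal stays near nominal: 4.6% in total at 4%/4% and 5.1% at 10%/10%.

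**The case against.** The strongest reply is that the SAP never says patients leave the denominator. The FAS is all randomized, and a patient whose visit is filtered out or absent could be counted as not having shown clearing, with no imputation needed. That reading is possible, but the SAP does not state it. It would also turn an observed clearing at Visit 3 into a failure for a patient who stopped study drug without rescue, which no protocol text supports.

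The protocol is itself divided. The missing-data rule is only in the synopsis, and the primary estimand in 9.1.10 assumes continued treatment, which an on-drug filter might be meant to serve. The same estimand sentence disregards actual compliance, however, which points the other way. The division is a reason to reconcile both documents. Using the observed value for off-drug patients is a choice the protocol leans towards but does not spell out.

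Two points on size stand. At the only documented loss rate the rules almost agree. Also, step 2 applies 22% and 7% to all 210 patients, whereas the plan applies them to 202 evaluable patients. On that basis, counting 4% losses as failures gives 21.1% against 6.7% at 140/70 and 81.4% power; dropping the losses gives 81.6% at 134/67. The conclusion is unchanged.

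The planned blind data review (SAP 6.2) and sensitivity analyses (SAP 6.3.7) are partial safeguards. Neither fixes the primary rule, and the sensitivity analyses are not defined.

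**Conclusion.** The concern holds and should be fixed before unmasking. The documents support different Day 8 denominators for the primary test, and the same gap affects the key secondary test. The contradiction needs no assumption. Its size does: the effect is negligible at equal 4% removal, while the assumed unequal removals give power from 68% to 94% and a difference from 14.4 to 20.1 points, against 83.4% and 15.0 with failures counted. The direction cannot be known in advance. When the removed patients are failures, clearly heavier removal on placebo costs power, and equal removal or heavier removal on clobetasol inflates the difference. In the one null case with heavier removal on clobetasol (20%/5%), the chance of a false finding for clobetasol rises from 2.0% to 4.6%.

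**What to change.** 1. Delete the filter sentence in SAP section 5 as the FAS rule. If the on-drug, no-rescue analysis is wanted, define it as a sensitivity analysis under Table 14.2.19.
2. State in SAP 6.3.5 and 6.6 that all randomized patients are in the Day 8 denominator, and that rescue before Visit 3 or a missing Visit 3 assessment counts as non-response. Carry the synopsis rule into protocol 9.1.3.
3. Apply the same missing-data rule to the key secondary endpoint in SAP 6.3.6.1, marked as an addition because the protocol states it only for the primary.
4. Use the observed Visit 3 value for patients off study drug without rescue, and state how non-rescue prohibited medication counts.
5. Analyse Day 15 and Day 29 whatever the study-drug status, and state how values after rescue are handled there.
6. Reconcile the estimand sentence in protocol 9.1.10 with the rule that rescue is failure.

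**Cost.** No new data or visits, since the protocol already asks patients off study drug to keep attending. The changes are to wording, but those to protocol 9.1.3 and 9.1.10 may need an amendment under section 9.2, and IRB approval under 11.4 if judged major. Reported response rates will be lower than under the filter wherever removed patients were failures, by an amount that depends on how many there are.

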#### 9.1.1 *Sample Size*

A two group  $\chi^2$  test with a 0.05 two-sided significance level will have 80% power to detect the difference between a proportion with complete resolution of anterior chamber cells in the active group of 0.22 and the placebo group proportion of 0.07 (odds ratio of 3.747) when the sample size is 202. Considering a 4% lost to follow-up rate a final sample size of 210 patients will be required (140 clobetasol, 70 placebo, in a 2:1 randomization ratio).

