### **9.1.10 Primary Analysis**

The aim of the primary analysis of this study is to assess the superiority of clobetasol propionate ophthalmic nanoemulsion 0.05% compared to placebo with respect to the primary endpoint in the FAS.

The primary analysis will be based on a single study eye for each patient. Each patient's study eye will be defined as the surgery eye.

The test will be the proportion of study eyes with complete clearing of anterior chamber cells (count cell = 0) at Visit 3 (Day 8 ± 1 day) without receiving rescue medication as compared between clobetasol propionate ophthalmic nanoemulsion 0.05% dosed QID and placebo dosed QID using the chi square statistic.

The PP population set will be also tested to confirm the robustness of the primary analysis.

The primary estimand (efficacy estimand) will be defined as the effect of the randomized treatments in all subjects meeting selection criteria assuming continuation of randomized treatments for the duration of the study regardless of actual compliance.

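### The Visit 3 per-protocol set drops rescued patients, whom the endpoint counts as failures, so it cannot serve as a robustness check on the FAS result

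*SAP*

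**What the plan says.** Protocol Section 6.7.2 fixes the status of rescue: "Rescued patients will be considered treatment failures, but the need for rescue therapy will not be considered an AE". The missing-data paragraph of the Protocol Synopsis says rescue does not create missing data, "since the primary measure is a responder measure where rescue is considered treatment failure". The primary and key secondary tests (Protocol 9.1.10 and 9.1.11; SAP 6.3.5 and 6.3.6.1) count a study eye as a success at Visit 3 only if the patient has not been rescued.

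On the purpose of the PP set, Protocol 9.1.10 states: "The PP population set will be also tested to confirm the robustness of the primary analysis". SAP Section 5 then builds the Visit 3 PP set for both tests from FAS patients with no eligibility violation, adequate compliance at Visit 3, and "without the use of rescue/prohibited medication until visit 3". The results go to Tables 14.2.1.2 and 14.2.2.2.

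Three other provisions bear on this:
- Protocol 5.3 and 6.7.2 say that a rescued patient stops the study medication.
- SAP Section 5 sets the compliance limit at 80%, and SAP 6.3.8 uses a fixed 32 planned doses at Visit 3.
- Protocol 6.7.1 makes the rescue drugs the same list as the prohibited drugs, told apart by being given for non-response. Protocol 9.1.4 lists prohibited medication as a PP violation.

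**The concern.** Rescue happens after randomization, is prompted by inadequate response, and is part of the definition of failure. Leaving rescued patients out of the PP set therefore selects on the outcome: each one removed is a certain non-responder. What remains is response among patients who did not need rescue, a group that treatment itself helps to define.

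A robustness check should ask the same question under a stricter view of conduct. This one asks a different question, so a PP result that differs from the FAS cannot be put down to protocol deviations, and one that agrees gives little reassurance. If placebo patients are rescued much more often, the check could fail to support a real effect.

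**Working it through.** **The plan's own figure.** Protocol 9.1.1 states that a chi-square "test with a 0.05 two-sided significance level will have 80% power to detect the difference" between an "active group of 0.22 and the placebo group proportion of 0.07 (odds ratio of 3.747) when the sample size is 202", allocated as "140 clobetasol, 70 placebo, in a 2:1 randomization ratio".
- Odds ratio: (0.22/0.78)/(0.07/0.93) = 3.747, as stated.
- Pooled rate at 2:1: (0.07 + 2 × 0.22)/3 = 0.17.
- Placebo n = [1.96√(1.5 × 0.17 × 0.83) + 0.8416√(0.07 × 0.93 + 0.22 × 0.78/2)]² / 0.15² = 67.1, so 68 placebo + 136 active = 204, against 202 stated.
- Power at 202 by the normal approximation is 80.2%. 202/0.96 = 210.4, against 210 stated.

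The design figure reproduces.

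**Effect of the PP clause.** Let r1 and r0 be the shares rescued by Visit 3 on active and placebo. Rescued patients contribute no successes, so removing them changes only the denominators:
- PP response rates: 0.22/(1 − r1) and 0.07/(1 − r0).
- PP sizes: 140(1 − r1) and 70(1 − r0), rounded.

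This makes two assumptions. The design rates already count rescue as failure (Protocol 9.1.1 and SAP 4.2 speak only of complete resolution of cells), and nobody is excluded for any other reason. All rescue rates below are assumed.

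Power comes from exact enumeration of the uncorrected two-sided 5% chi-square test. The last column keeps 0.22 and 0.07 and reduces only the sample size.

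| Rescue active/placebo | n | PP rates | Difference (points) | Power, rescued removed | Power, same n, rates unchanged |
|---|---|---|---|---|---|
| none | 140/70 | 22.0% / 7.0% | 15.0 | 83% | 83% |
| 5%/5% | 133/67 | 23.2% / 7.4% | 15.8 | 84% | 82% |
| 10%/10% | 126/63 | 24.4% / 7.8% | 16.7 | 85% | 80% |
| 20%/20% | 112/56 | 27.5% / 8.75% | 18.75 | 85% | 74% |
| 5%/10% | 133/63 | 23.2% / 7.8% | 15.4 | 80% | 80% |
| 5%/15% | 133/60 | 23.2% / 8.2% | 14.9 | 76% | 79% |
| 10%/30% | 126/49 | 24.4% / 10.0% | 14.4 | 60% | 71% |
| 10%/40% | 126/42 | 24.4% / 11.7% | 12.8 | 42% | 64% |

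Both response rates rise in every row with rescue. With equal rescue the difference widens and power edges up although patients are lost. With much more rescue on placebo, the difference narrows and power falls below what sample size alone explains. By the normal approximation, power breaks even when placebo rescue is about 1.11 times active rescue (5.55% against 5%; 11.1% against 10%).

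**Second route out of the set.** 80% of 32 doses is 25.6, so 26 doses are needed, or 26/4 = 6.5 days at four a day. A patient who stops study medication on rescue before then fails the compliance rule too. Deleting the rescue phrase alone would therefore leave many rescued patients excluded.

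**The case against.** The strongest reply is that this is what a PP set is for: it shows the effect when treatment is taken as intended. Protocol 9.1.4 already lists prohibited medication as a violation, and rescue drugs are drawn from that list. The FAS is primary, nothing requires the PP test to be significant, and SAP 6.3.7 foresees sensitivity analyses for rescue.

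Much of this stands. The analysis is supportive, and the SAP's exclusion follows from the protocol's own definition, so both texts need attention. But an ordinary PP exclusion removes patients whose outcome is uninterpretable. Here the outcome is settled by definition. The planned sensitivity analyses name rescue as an intercurrent event but define no handling that would correct the PP rule.

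A reader might infer that the clause necessarily costs power or shrinks the treatment contrast. The documents do not support that. They give no rescue rate, equal rescue raises both power and difference, and 5%/10% leaves power at 80% with a larger difference. More rescue on placebo is plausible, because rescue follows non-response and the vehicle is expected to do worse, but it is not quantified. Nor is the whole fall from 83% due to selection: at 10%/30%, sample size alone takes power to 71%.

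The two exclusion routes do not double the harm, since a patient leaves the set once. They matter because the fix must close both.

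**Conclusion.** The point holds as one about interpretation. Followed exactly, the Visit 3 PP analysis deletes certain non-responders, inflates response in each arm by 1/(1 − rescue share), and cannot be read as a check on the FAS result. That conclusion needs no assumed rate.

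The size and direction do. Under the stated assumptions exact power runs from 85% with equal rescue of 10–20% to 42% at 10%/40%, against 83% with nobody removed. Where placebo rescue is much higher, the bias runs against the active arm: the risk is failure to confirm a true effect. It would be wrong to conclude that such a pattern manufactures a favourable result, or that the PP clause lowers the power of the primary test, since the FAS analysis does not depend on it.

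The correction should be made, but it concerns a supportive analysis.

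**What to change.** In SAP Section 5, define the Visit 3 PP set so that:
- patients whose only departure is rescue for non-response stay in and are counted as non-responders for both endpoints;
- their compliance is computed up to the rescue date, not against the fixed 32 doses;
- exclusion is limited to entry violations, non-compliance unrelated to rescue, and prohibited medication not given for non-response.

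Make the PP definition in Protocol 9.1.4 consistent with this, for example by stating that rescue for non-response is not a prohibited-medication violation for this purpose. SAP 6.3.9 already separates rescue, as recorded in the eCRF, from prohibited medication, so no new data are needed.

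At the same time, reconcile the nearby sentence in SAP Section 5 that limits FAS efficacy analyses to visits on study medication and free of rescue or prohibited drugs. Read literally, it would drop rescued patients' visits from the primary analysis too, contrary to rescue counting as failure. This is a separate and weightier matter, but the same edit should settle it.

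The cost is wording in the SAP and an aligned protocol definition, settled before unmasking. It concerns analysis-set membership only and changes no treatment or rescue rule.
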